Impact of an IMB theory-based health education intervention on hypoglycemic coping in patients with type 2 diabetes: a pilot study

August 01, 2023

Study Protocol

1. Integrity Statement

(1) Ensure that the operation is in strict accordance with the test protocol and the authenticity of the data records; (2) No conflict of interest with other projects.

2. Title of the study

Impact of an IMB theory-based health education intervention on hypoglycemic coping in patients with type 2 diabetes: a pilot study

3. Flow chart of the implementation of the study

Specific intervention program for T2DM hypoglycemic coping styles based on IMB modeling

Level 1 indicators	Level 1 indicators	Level 1 indicators (Content of the intervention)	Objectives of intervention	Forms of intervention	intervention time	implementers
information	base case	Patients completed the questionnaire within 3 hours of admission.	1、 Perfect hypoglycemic cognition. 2 、 Correct incorrect hypoglycemic cognition and rebuild the hypoglycemic cognitive system. 3 、 Re-understand the different outcomes of different hypoglycemic coping styles. 4、 Master the skills of hypoglycemic coping styles. 5、 Improve the negative cognition, positive coping.	poll	Within 3 hours of admission	nurse practitioner-in-charge
	Hypoglycemia Handbook	Distribute hypoglycemia brochures and assist patients in developing individualized blood glucose management plans.		written form	Day 1 of admission	nurse practitioner-in-charge
	Specialized Lectures	Centralized in-departmental hypoglycemia education in the form of a PowerPoint presentation by a specialist nurse.		PPT (location: demonstration room, time: 8 minutes)	Day 2 of admission	Principal Investigator
	peer education	Introduce patients to recognize the pre-symptoms of hypoglycemia and how to deal with them, and show the dangers of wrong ways of coping with hypoglycemia with examples. Utilize the peer effect to allow people to share their experiences of hypoglycemia management and exchange experiences.		PPT presentation (15min) Peer exchange (20min)	3rd day of admission (and every Friday afternoon thereafter, after the end of treatment)	Principal Investigator
	WeChat Information Dissemination	Patients and their families join the WeChat group on admission, and every Tuesday and Thursday, we push out the graphic and video knowledge related to diabetes mellitus hypoglycemia (the content involves diabetes mellitus specialty knowledge, diet, exercise, blood glucose testing, hypoglycemia coping, psychological debugging, etc.).		WeChat form	From the first week of admission	Principal Investigator and Charge Nurse

	Knowledge Contest with Prizes	Conduct a contest on knowledge related to coping with hypoglycemia, with small gifts awarded to the top three winners.		In the form of a group activity (duration: 30 minutes)	1 day before discharge	Principal Investigator
motives	Health belief formation	Based on the results of the patient's hypoglycemic coping style questionnaire on admission, the intervener will give corrections for the diabetic patient's misperceptions, assist in setting goals for the next week, and give positive psychological interventions	1、(No-intention period) Change their negative hypoglycemia coping mentality and establish correct health beliefs. 2、(Intentional period) Enhance their confidence in coping with hypoglycemia positively and recognize the harm of negative coping.	Questionnaires, one-on-one exchanges (20 minutes long)	Day 1 of admission	nurse practitioner-in-charge
	Family member support	Face-to-face communication with patients and their families was conducted 1 day before discharge to understand the family status of the patients after discharge and inform their families of the importance of family support in coping with diabetes mellitus, instructing the patients' families to control their diets and their behaviors, to do a good job of family support, to play a good supervisory and nursing care, and at the same time, informing the patients of the path of professional counseling and the convenience of the community resources and so on.	1、(Preparation period) Include family members and act together to provide family support for patients 2、(Change period) Make full use of resources at home, hospitals, communities, pharmacies, etc. to promote behavioral change 3、(Sustainability Period) Guide patients to think about the benefits gained from healthy behaviors, instruct them	Face-to-face exchanges (20 minutes in length)	1 day before discharge	nurse practitioner-in-charge
	Medical staff support	1, 2, 3 weeks after discharge, every Tuesday and Thursday through the WeChat group to push the knowledge related to diabetic hypoglycemia, and encourage patients to actively share their own experience of successfully coping with hypoglycemia in the group, in order to play the role		WeChat or Phone	1, 2, 3 weeks after discharge	Principal Investigator

		
of an example. For patients with difficulties in coping, contact them by phone or WeChat, and according to the actual situation of the patients, analyze the reasons and assist in the development of a coping plan, and modify the plan in a timely manner according to the actual situation of the patients during the implementation of the plan.
	
to effectively use social and family resources, and establish internal and external environments conducive to the long-term implementation of the program to encourage patients to continue to adhere to it.
			
	social security (pensions, medical insurance)	
The group education and feedback were conducted in the 4th week after discharge from the hospital at the Diabetes Clinic of Chuzhou First People's Hospital.
		
Group offline lectures (duration: 1 hour)
	
4th week after discharge
	
Principal Investigator

behavioral skill	Health Information Access Skills	
Patients are admitted to the hospital for an explanation of ways to acquire knowledge about diabetes, and the WeChat group pushes out specialized websites for patients to view, or they can go to the hospital's diabetes specialist clinic for consultation.
	
1、Guide them to adopt a correct and scientific way of obtaining disease information.
 
2、Enhance the coping ability to deal with hypoglycemia.
 
3、Perform diabetes outpatient information consultation and sensitization, so that they can obtain professional knowledge in the professional window.
 
4、Guide patients with psychological disorder to moderate psychological counseling in order to enhance confidence.
	
Questionnaire, PPT presentation, WeChat
	
Day 2 of admission
	
nurse practitioner-in-charge

	Self-conditioning skills	
Post-discharge WeChat pushes examples of the dangers of incorrect response to hypoglycemia on Tuesdays and Thursdays, as well as knowledge of insulin injection techniques, diet, exercise skills, and blood glucose testing; patients are asked to keep a diabetes diary every month.
		
WeChat, written
	
1, 2, 3 months after discharge
	
nurse practitioner-in-charge

	Peer experience sharing	
Regular monthly communication with discharged patients, patients with more serious problems, one-on-one communication at the end of the lecture, weekly and monthly plans; praise for better performance and let them talk about their coping experience.
		
Lecture (duration: 1 hour)
	
1, 2, 3 months after discharge
	
Principal Investigator

4. Background

Hypoglycemia, as one of the common complications in patients with diabetes mellitus, not only leads to an increase in the incidence of cardiovascular events and all-cause mortality, but also imposes a serious psychological burden on them, so much so that patients make behavioral changes such as increasing food intake, decreasing insulin dosage, and restricting physical activity in order to prevent hypoglycemia, which are not conducive to the management of the disease and accelerate the adverse regression of the disease, therefore, it is urgent to change the erroneous Hypoglycemic coping is urgent, and IMB theory, which states that individuals must have three behavioral components, namely information, motivation, and behavioral skills, in order to produce behavioral change, can help interveners to analyze the behavioral components that are lacking in order to determine the focus of the intervention, select appropriate interventions, and implement them. The purpose of this study was to develop a health education intervention program based on the IMB theory to change erroneous hypoglycemic coping styles and to validate the feasibility, acceptability, and initial effectiveness of the program.

5. Research purpose

The purpose of this study was to develop a health education intervention program based on the IMB theory to change the erroneous hypoglycemic coping styles of patients with type 2 diabetes and to validate the feasibility, acceptability, and initial effectiveness of the program.

6. Inclusion and Exclusion Criteria

Inclusion criteria: (1) meet the 2018 edition of ADA Diabetes Medical Diagnosis and Treatment Criteria and diagnosed with T2DM; (2) patients using insulin or sulfonylureas; (3) disease duration ≥ 1 year, age ≥ 18 years; (4) history of hypoglycemia occurrence in the past 6 months; (5)

patients with a tendency of avoidance and compromise in T2DM Hypoglycemic Coping Styles Inventory; (6) good communication and verbal skills; (7) have a smartphone and know how to use it; and (8) voluntarily participate in this study. Exclusion Criteria: (1) patients with type 1 diabetes mellitus; (2) patients with severe complications in combination with T2DM; and (3) patients who are participating in studies on other topics.

7. Intervention process

From August 2023 to January 2024, T2DM patients who met the inclusion and exclusion criteria were selected from 1 tertiary hospital in Chuzhou City. The control group implemented conventional diabetes health education, and the intervention group implemented health education based on IMB theory on the basis of the control group.

8. Sample size estimation

In this study, a randomized controlled trial was conducted to investigate the effect of intervention based on IMB model on the hypoglycemic coping style of T2DM patients, which was randomly divided into the control group and the intervention group, and the main observation index was the hypoglycemic coping style after the intervention. According to previous studies in similar literature, the control group was 30.14 ± 5.08 , and the intervention group was 34.40 ± 5.36 , with $\alpha = 0.05$, power = 0.95, and 1:1 parallel control. According to the formula for calculating the sample size of the mean value of the two groups, the sample size of the two groups was calculated to be 41 cases in each group, and at least 50 cases should be included in each group at the baseline, taking into account the 15% dropout rate, which made the total number of cases to be 100 in total.

9. Randomisation

Participants were identified through screening of medical records and face-to-face interviews, and participants signed a written consent form to participate in the study. After the baseline assessment, participants were randomly assigned to either the intervention or control group using a lottery method after drawing a labelled card in an opaque sealed envelope from an independent research assistant who was not involved in the recruitment and implementation of the study.

10. Measurement index

General information questionnaire: day 1 of admission; Hypoglycemia Coping Styles Scale for Patients with Type 2 Diabetes Mellitus (primary indicator): day 1 of admission, 4 weeks post-intervention, 8 weeks post-intervention, and 12 weeks post-intervention; Fear of Hypoglycemia Scale Score (secondary indicator): day 1 of admission, 4 weeks post-intervention, 8 weeks post-intervention, and 12 weeks post-intervention; Health Information Acquisition Behavior Scale (secondary indicator): day 1 of admission, 4 weeks post-intervention Day 1, 4 weeks post-intervention, 8 weeks post-intervention, 12 weeks post-intervention; Type 2 Diabetes Knowledge Scale (secondary indicator). Day 1 of admission, 4 weeks post-intervention, 8 weeks post-intervention, and 12 weeks post-intervention.

11. Ethical consideration

The study was ethically approved by the Ethics Committee of the College of Nursing of Yangzhou University (YZUHL20220047).

12. Statistical analysis of data

SPSS 26.0 software was applied for data analysis. Describing the general demographic characteristics of the study population: Mean \pm standard deviation ($\pm s$) was used to describe measures that conformed to normal distribution, and median and interquartile spacing M (QR) were used to describe skewed distribution; count data were expressed as frequencies and constitutive ratios. Homogeneity test: the chi-square test or Fisher's

exact test was used for the count data of the two groups at baseline, non-parametric test was used for the rank count data, and t-test or non-parametric test was used for the measurement data. Repeated measures ANOVA was used to analyse the intervention effect of each indicator within groups, and two independent samples t-test was used to compare between groups at different time points before and after the intervention. The significance level $P < 0.05$ indicated that the difference was statistically significant.

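### Section 12 gives the name of intervention effect to a within-group ANOVA and does not say which between-group comparison, at which visit, decides efficacy

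*Combined protocol and SAP*

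**What the plan says.** Section 12 describes two analyses in one sentence. The first is "Repeated measures ANOVA was used to analyse the intervention effect of each indicator within groups". The second is "two independent samples t-test was used to compare between groups at different time points before and after the intervention". Every test is judged at P < 0.05. The plan gives no group-by-time term, baseline adjustment, primary contrast or multiplicity rule.

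Other sections bear on how these analyses can be read:

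- Section 8 says "the main observation index was the hypoglycemic coping style after the intervention" and gives no week.
- Section 10 lists "Hypoglycemia Coping Styles Scale for Patients with Type 2 Diabetes Mellitus (primary indicator): day 1 of admission, 4 weeks post-intervention, 8 weeks post-intervention" and then 12 weeks. None of the three follow-up visits is called primary.
- Section 7 says "the intervention group implemented health education based on IMB theory on the basis of the control group", so both arms receive conventional education.
- Inclusion criterion 5 in section 6 admits "patients with a tendency of avoidance and compromise in T2DM Hypoglycemic Coping Styles Inventory".
- Section 9 says "After the baseline assessment, participants were randomly assigned to either the intervention or control group", so the baseline score is known before allocation and can be adjusted for.

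**The concern.** The randomised question is whether the arms differ. A repeated-measures ANOVA run inside one arm asks only whether that arm's mean changes over time. The two can part company here for two reasons.

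1. The intervention is added to conventional education, so change in the intervention arm includes whatever usual education achieves.
2. Patients are selected on a coping-styles inventory, taken here to be the primary scale. The only coping questionnaire described before randomisation is the one at admission (section 3 refers to the "hypoglycemic coping style questionnaire on admission, the intervener will give corrections" made on its results). If that one administration serves for both eligibility and baseline, regression to the mean will produce apparent improvement in either arm.

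As written, a significant time effect in the intervention arm, or in one arm and not the other, could be reported as effectiveness. So could significance at any one of three follow-up t-tests. Neither rule holds a 5% error rate for the trial's question.

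**Working it through.** **The plan's own sample size.** Inputs from section 8: means 30.14 and 34.40, SDs 5.08 and 5.36, alpha 0.05, power 0.95, 1:1.

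- Difference: 34.40 − 30.14 = 4.26.
- SD: √((5.08² + 5.36²)/2) = 5.22. Standardised difference: 4.26/5.22 = 0.816.
- Normal formula: n = 2(1.960 + 1.645)²/0.816² = 39.1, so 40 per group. With the t distribution it is 41, with power 95.4%.
- Dropout: 41/0.85 = 48.2, so 49, close to the planned 50.

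The stated 41 is reproduced by a two-sided test (one-sided, t-based, would need 34). Section 8 therefore sizes one between-group comparison of means at one time.

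**Simulation set-up.** 20,000 to 40,000 trials per case; 42 per arm (50 × 0.85 = 42.5); four visits; normal scores; no between-group effect. Assumed, because the documents do not give them: equal between-visit correlation of 0.6, 0.7 or 0.8; the size of any shared gain; the eligible fraction; and 5.22 as the SD before selection. Higher scores are taken as better, as the section 8 means imply.

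**Within-arm ANOVA (Greenhouse-Geisser), share of arms with P < 0.05:**

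| Case | corr. 0.6 | corr. 0.7 | corr. 0.8 |
|---|---|---|---|
| Shared gain of 1 point, no selection | 24% | 32% | 47% |
| Shared gain of 2 points, no selection | 80% | 91% | 98% |
| Lower two thirds eligible on the baseline score | 33% | 25% | 17% |
| Lower half eligible on the baseline score | 67% | 52% | 34% |

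With no selection and no gain the rate is 4.5-4.6%. With selection on a separate, equally correlated administration it is 4.2-4.7%.

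The selection rows follow from the apparent gain, (1 − correlation) × λ × SD, where λ is the distance in SDs of the selected group's mean below the population mean.

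- Lower half, λ = 0.798: 0.4 × 0.798 × 5.22 = 1.67 points at correlation 0.6, and 0.2 × 0.798 × 5.22 = 0.83 at 0.8.
- Lower two thirds, λ = 0.545: 1.14 and 0.57 points.

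Under selection, one arm is significant and the other not in 28-44% of trials (lower two thirds) or 44-50% (lower half).

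**Between-group t-tests.** At 12 weeks alone the error rate is 4.7-5.4% in every case. For at least one of three, independence would give 1 − 0.95³ = 14.3%. With the assumed correlations the simulated figure is 10-12% without selection and 11-13% with it.

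**Baseline-adjusted 12-week contrast (ANCOVA), under selection.** Error is 4.7-5.3%. Its variance relative to the t-test is approximately (1 − ρ²)/(1 − ρ²(1 − k)), where ρ is the correlation and k is the fraction of baseline variance left after selection (0.363 for the lower half, 0.468 for the lower two thirds).

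- Largest ratio, lower half at ρ = 0.6: 0.64/(1 − 0.36 × 0.637) = 0.83 (simulated 0.84).
- Smallest ratio, lower two thirds at ρ = 0.8: 0.36/(1 − 0.64 × 0.532) = 0.55 (simulated 0.55).

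The variance is thus 16-45% lower, and 42 per arm act like 42/0.84 = 50 to 42/0.55 = 76.

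**The case against.** Read together, sections 8, 10 and 12 point to a between-group t-test on the coping scale as the efficacy test. Section 8 sizes that comparison and section 12 plans it. On this reading, the wording about the within-group ANOVA may be a translation slip, and only the visit is missing. No passage says that a within-arm P value, or any single visit, is enough. The trial is also a pilot.

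Much of this is fair. The t-tests are valid randomised comparisons. A significant time effect when both arms truly gain is a correct answer to the ANOVA's own question, and becomes an error only when it is read as efficacy. The wording still invites that reading, and even on the kindest view no visit is named. The pilot label softens the consequence, but a first look at effectiveness is a stated aim and section 8 asks for 95% power.

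The percentages also depend on assumed inputs. At correlation 0.3 the shared-gain figures fall to about 15% (1 point) and 53% (2 points), while the selection figures rise to 59% and 95%. Criterion 5 may classify a coping style and not cut a total score. Section 9 also leaves room for separate screening and baseline administrations, in which case selection does no harm.

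Baseline adjustment is a gain in precision and is not needed for validity. A model with one common baseline slope is not identical to a 12-week ANCOVA, but in simulation it gives essentially the same variance.

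One further point stands. Section 3 schedules programme activities up to three months after discharge, so the date from which the post-intervention weeks are counted needs stating.

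**Conclusion.** The concern holds. Section 12 attaches the treatment-effect label to an analysis that cannot estimate one, and no section names the deciding contrast or visit. That follows from the text and needs no assumption.

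The firmest figure is the 10-13% chance of at least one false positive among three follow-up t-tests, about double the nominal 5%. The within-arm figures show how misleading that analysis could be if read as efficacy. A shared gain of 1 point, under a quarter of the planned 4.26, is enough to raise the rate to 24-47% at correlations of 0.6 to 0.8. The selection figures apply only if eligibility and baseline share one administration of the primary scale.

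This should be fixed, but it is not a flaw in the design or the sample size: a single-visit t-test with 41 per group keeps 95.4% power.

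**What to change.** Replace the sentence in section 12 with wording such as:

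> Each scale is analysed with one linear mixed model (SPSS MIXED) in all randomised participants with follow-up data, in the group to which they were randomised. The outcomes are the 4-, 8- and 12-week scores. Fixed effects are group, visit, group-by-visit and baseline score, with an unstructured covariance over the three visits. The intervention effect is the adjusted between-group mean difference at 12 weeks post-intervention, with its 95% CI. The 4- and 8-week differences are secondary. Within-group change is reported descriptively and is not called an intervention effect.

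The 12-week visit is a proposal. If the sponsor prefers another, the SAP should name it before the data are analysed. In either case it should state the date from which the weeks are counted.

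If success at any one of the three visits is really intended, that needs an explicit multiplicity rule. With Bonferroni (0.05/3), 95% power takes 50 evaluable per group, or 50/0.85 = 58.8, so 59 recruited; 41 per group would give about 90%.

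The proposed change costs SAP wording and a little analysis work. It needs no extra patients, visits or measurements, and keeps the planned software.

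### No analysis population or missing-data rule is stated, so with 15% dropout planned the named tests default to whoever is present at each visit

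*Combined protocol and SAP*

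**What the plan says.** Section 12 names two analyses of effect, one within groups and one between groups: "Repeated measures ANOVA was used to analyse the intervention effect of each indicator within groups, and two independent samples t-test was used". The between-group part reads in full: "two independent samples t-test was used to compare between groups at different time points before and after the intervention". The software is SPSS 26.0.

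Section 10 schedules the primary coping scale at "day 1 of admission, 4 weeks post-intervention, 8 weeks post-intervention, and 12 weeks post-intervention", so each patient should have one baseline and three follow-up scores. Section 9 places randomisation after the baseline assessment, so every randomised patient should have a day-1 score.

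Section 8 expects losses: "at least 50 cases should be included in each group at the baseline, taking into account the 15% dropout rate".

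No section defines an analysis population, mentions intention-to-treat, or gives an imputation method, a missing-data assumption or a sensitivity analysis.

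**The concern.** When a plan expects dropout but gives no rule for it, the named methods settle the matter by default. A two-sample t-test at 12 weeks can use only patients with a 12-week score. A patient who left after week 4 counts in the 4-week test, but the 12-week estimate ignores what is already known about that patient. Classical repeated-measures ANOVA in SPSS needs all four scores and removes anyone missing one. The two analyses can therefore describe different patients, and each visit's t-test can compare a different subset of those randomised.

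This matters most if loss depends on response in one arm. Section 3 gives the intervention arm twice-weekly WeChat material, a group session in week 4 after discharge, one-hour monthly lectures and a monthly diary, up to three months after discharge. Section 7 gives the control arm conventional education only. If intervention patients who are not improving stop returning scales, the remaining intervention mean is too high and the 12-week difference overstates the effect. Raising the recruitment target to 50 per group protects power but does not correct this.

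**Working it through.** **Inputs from the documents (sections 8 and 10).** Control "the control group was 30.14 ± 5.08"; intervention 34.40, SD 5.36; alpha 0.05; power 0.95; 1:1 allocation; 41 per group evaluable; 50 per group recruited; 15% dropout; visits at day 1 and at 4, 8 and 12 weeks.

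**1. The plan's own figure.**
- Difference: 34.40 − 30.14 = 4.26.
- Pooled SD: √[(5.08² + 5.36²)/2] = 5.22.
- Normal approximation, two-sided: n = 2 × [5.22 × (1.960 + 1.645)/4.26]² = 39.05, so 40 per group.
- Noncentral t: power is 0.9498 at 40 and 0.9544 at 41, so 41 per group. The stated figure reproduces.
- Dropout: 41/0.85 = 48.2, so 49 are needed. The planned 50 covers this.

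**2. What remains at 12 weeks.** 50 × 0.85 = 42.5 per group, or about 85 of 100. Power for 4.26 is 0.959 with 42 per group and 0.962 with 43. The sample size is adequate.

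**3. Size of the bias under strong selection (assumed).** The documents give neither a dropout mechanism nor a correlation between visits. Assume no true effect, normal scores with SD 5.22, visit correlation ρ of 0.5 to 0.7, random dropout in the control arm, and intervention dropouts who all have below-median 4-week scores. The mean of the lower half of a normal distribution is −√(2/π) = −0.798 SD. If a fraction p is lost, the 12-week mean of those remaining rises by ρ × 5.22 × 0.798p/(1 − p).
- p = 0.15: 0.798 × 0.15/0.85 = 0.141 SD, giving 0.37 points (ρ = 0.5) to 0.51 points (ρ = 0.7).
- p = 0.20 (against 10% in control): 0.798 × 0.20/0.80 = 0.200 SD, giving 0.52 to 0.73 points.

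Simulation (4,000 trials per scenario, 50 per arm) agrees:
- 15% lost in each arm: bias 0.35 to 0.53 points, type I error about 6% to 8%.
- 20% against 10% lost: bias 0.51 to 0.74 points, type I error about 7% to 10%. Here 0.74/4.26 = 17%.

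**4. Milder selection (assumed).** Dropout odds 1.5 to 2 times higher per SD lower 4-week score, 16% lost per arm.
- Selection in the intervention arm only: bias about 0.17 to 0.39 points, type I error about 5% to 7%.
- Same selection in both arms: bias within 0.03 of zero.

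**5. What the collected scores can recover.** Under the mechanism in step 3, an estimate using the observed day-1 and 4-week scores, standardised to all randomised patients, had bias of at most 0.04 points. With day-1 scores alone, 0.16 to 0.27 points remained. These runs used regression, not the mixed model proposed below, and gave every dropout an observed 4-week score. They show the value of the scores when loss depends on observed data.

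**6. What they cannot recover.** Suppose loss of 15% in the intervention arm depends on the 12-week score itself, with odds ratios of 1.5, 2 and 3 per SD lower. The mean of those remaining then shifts by 0.060, 0.098 and 0.143 SD; multiplied by 5.36, this is 0.32, 0.53 and 0.77 points. Separately, if completers differ by 4.26 and intervention dropouts gain nothing, with equal dropout in both arms, the all-randomised difference is 0.85 × 4.26 = 3.62, which is 0.64 points lower. Only a sensitivity analysis can address such cases.

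**The case against.** Three points stand against a stronger reading.

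First, a reader might infer that the plan excludes dropouts and replaces the randomised comparison with a completer analysis. Section 12 does not say so. It is silent, and filling in values before either test is not ruled out. The between-group t-tests are available-case at each visit. At 12 weeks they use the patients still present, but the 4-week test keeps those lost later. Listwise deletion belongs to the ANOVA, which is described as within groups and does not produce the between-group estimate.

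Second, a reader might infer that the result will favour the intervention. The documents give no dropout by arm. Section 3 also gives the intervention arm phone or WeChat contact for patients having difficulty and one-to-one discussion for more serious problems, which could retain the poor responders assumed to leave. Similar selection in both arms leaves almost no bias.

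Third, this is a pilot, and the bias is modest against 4.26. Even under the strong mechanism the planned effect would still be detected, with power of about 98% to 99%; its size would be overstated.

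What remains is the gap itself. The pilot's aims include initial effectiveness, it is powered at 0.95, and it tests at P < 0.05, so how missing scores are handled bears on its main claim.

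**Conclusion.** The concern holds as a gap in specification with a predictable default: no analysis population, no missing-data rule, and named methods that use available cases. About 15 of 100 randomised patients would be missing from the 12-week comparison, and their earlier scores would go unused there.

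The bias cannot be computed from the documents. As an illustration, with selection in the intervention arm only, it is about 0.2 to 0.4 points under mild selection on the 4-week score and 0.4 to 0.7 points under strong selection, or up to about 17% of 4.26. Type I error is then about 5% to 10%. These ranges rest on the assumed mechanisms, dropout split and visit correlation. The change should be made, but the gap does not by itself invalidate the trial.

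**What to change.** In section 12:
- State that all randomised patients are analysed in their assigned arm.
- For the primary and secondary scales, replace the per-visit t-tests and within-group ANOVA with one linear mixed model (SPSS MIXED) that keeps every available score.
- Enter the day-1 score as an outcome with a common baseline mean in both arms. Include visit and arm-by-post-baseline-visit effects and an unstructured covariance. A model with only follow-up scores as outcomes would leave out patients lost before week 4. Multiple imputation from the day-1 score is an acceptable alternative.
- Report the between-arm difference at each visit. Within-arm changes come from the same model.
- Add one delta-adjusted sensitivity analysis that lowers the missing intervention-arm scores, for example by 0 up to 4.26 points. At 15% missing, the largest shift moves the 12-week difference by 0.15 × 4.26 = 0.64 points.

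The cost is a few sentences and slightly more analysis work, with no new patients, visits or data. The main model relies on a missing-at-random assumption, which the sensitivity analysis probes.

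### The primary coping scale is tested between groups at weeks 4, 8 and 12, each at P<0.05, with no visit named as primary; if any visit counts, the false-positive rate is about 0.08 to 0.14, not 0.05

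*Combined protocol and SAP*

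**What the plan says.** Section 8 (Sample size estimation) states that "the main observation index was the hypoglycemic coping style after the intervention", without naming a week. It sizes a single comparison of two means "with $\alpha = 0.05$, power = 0.95, and 1:1 parallel control", giving 41 per group, raised to 50 per group for 15% dropout. The source of the means is given as "According to previous studies in similar literature, the control group was 30.14" (SD 5.08), against 34.40 (SD 5.36) with the intervention. Which score of the scale these figures describe is not said.

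Section 10 (Measurement index) lists the Hypoglycemia Coping Styles Scale as "primary indicator): day 1 of admission, 4 weeks post-intervention, 8 weeks post-intervention, and 12 weeks post-intervention". That is one baseline and three follow-up assessments.

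Section 12 (Statistical analysis of data) assigns two methods. For change over time: "Repeated measures ANOVA was used to analyse the intervention effect of each indicator within groups". For the comparison of arms: "two independent samples t-test was used to compare between groups at different time points before and after the intervention". One threshold serves every test: P<0.05 "indicated that the difference was statistically significant".

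**The concern.** The sample size belongs to one test, but the analysis section specifies three post-baseline between-group tests of the same primary scale and does not say which one decides. No overall between-group test stands in front of them, because the ANOVA looks only within groups.

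The visit that carries the primary conclusion can therefore be chosen after the results are seen. Two unwritten rules are possible, and section 8's pair of alpha 0.05 and power 0.95 describes neither. If one significant visit is enough, alpha rises. If all three visits must be significant, power falls.

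Two further gaps prevent a reader from identifying a single primary test. The score behind the section 8 means is not named. The weeks counted from the intervention have no stated origin, although the flow chart in section 3 schedules components at "1, 2, 3 months after discharge", which overlaps the follow-up period if weeks run from discharge.

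**Working it through.** **Inputs.** From section 8: means 30.14 and 34.40, SDs 5.08 and 5.36, alpha 0.05, power 0.95, 41 per group, 15% dropout. From section 10: three post-baseline visits. Assumed, because the documents are silent: two-sided tests, and a common correlation ρ between visits of 0 to 0.9. The baseline t-test is left out of the count, since it cannot support a claim of efficacy.

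**Step 1: reproduce the plan's figure.**
- Pooled SD = √((5.08² + 5.36²)/2) = 5.222.
- Difference = 34.40 − 30.14 = 4.26, so d = 4.26/5.222 = 0.816.
- The two-sided t-test at 0.05 with 95% power needs 40.04 per group, rounded up to 41. This matches the plan. A one-sided test would need 33.22, so the plan's figure implies a two-sided test.
- Dropout: 41/0.85 = 48.2, so 49, consistent with enrolling at least 50.
- Power of one two-sided t-test at 41 per group (80 df) is 0.954.

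The stated sample size therefore supports exactly one two-sided test at 0.05.

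**Step 2: false-positive rate if any visit counts.** At ρ = 0 the rate is 1 − 0.95³ = 0.143. For equally correlated visits, with c = 1.96,

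P(any) = 1 − ∫ φ(u) [Φ((c − √ρ·u)/√(1 − ρ)) − Φ((−c − √ρ·u)/√(1 − ρ))]³ du.

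Dropping the second Φ term gives false claims of benefit only, for which the nominal rate for one test is 0.025.

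| ρ | Any visit, either direction | Any visit, benefit direction |
|---|---|---|
| 0 | 0.143 | 0.073 |
| 0.3 | 0.136 | 0.068 |
| 0.5 | 0.125 | 0.063 |
| 0.7 | 0.109 | 0.055 |
| 0.9 | 0.084 | 0.042 |

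Simulated t-tests with 41 per arm agree to within about 0.003. A first-order autoregressive correlation gives slightly higher rates (0.130 at 0.5, 0.088 at 0.9). Even at ρ = 0.99 the equal-correlation rate is 0.060.

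**Step 3: power under each rule.** Simulation with 41 per arm, d = 0.816 at every visit:

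| ρ | Any visit at 0.05 | All three at 0.05 |
|---|---|---|
| 0.3 | 0.999 | 0.881 |
| 0.5 | 0.996 | 0.892 |
| 0.7 | 0.990 | 0.905 |
| 0.9 | 0.978 | 0.927 |

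The any-visit rule loses no power; its cost is in alpha. The all-three rule has a false-positive rate of at most about 0.023 for ρ up to 0.9; its cost is in power.

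**The case against.** The plan nowhere says that one significant visit establishes efficacy. The inflation belongs to one reading of a silent text, and under the other reading alpha is not inflated at all. This is fair: the defect is the missing rule, and the error rates show what that silence permits.

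The correlation is assumed. Scores on one scale in the same patients four weeks apart are unlikely to be uncorrelated, so 14.3% is better seen as an upper bound. Over 0.5 to 0.9 the rate is 12.5% to 8.4%. That narrows the range without bringing it down to 5%.

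The trial is called a pilot, with aims of feasibility, acceptability and initial effectiveness, and strict error control matters less in that setting. This bears on how serious the point is. It does not remove it, because section 8 sizes a formal hypothesis test with 95% power and section 12 declares significance at P<0.05.

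Finally, if the section 8 effect is real at every visit, most rules would succeed: Holm keeps 94% to 99% power for at least one visit. That also stands. The gap matters mainly when the effect is absent or small, which is when a false claim can arise.

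The unnamed score and the undefined week origin do not themselves create multiplicity. They matter here because a single primary test cannot be written without them.

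**Conclusion.** The concern holds and should be fixed. Sections 8, 10 and 12 together specify three between-group tests of the primary scale, each at 0.05, with no primary visit, overall between-group test or multiplicity rule, while the sample size assumes one test.

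If any visit may count, the two-sided false-positive rate is about 0.08 to 0.14, and false claims of benefit run at about 4% to 7% against 2.5%. If all three are required, power is about 88% to 93% (ρ 0.3 to 0.9) rather than 95%. These figures assume two-sided tests, normal scores, between-visit correlations up to 0.9 and, for power, the section 8 effect at every visit with 41 evaluable per arm. The existence of the gap depends on none of these assumptions.

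**What to change.** Name one primary between-group test, in the same terms, in sections 8, 10 and 12. For example: *The primary endpoint is the between-group difference in [the total or named subscale score on which the section 8 means are based] at the 12-week assessment, with weeks counted from [stated starting point], tested two-sided at 0.05.* Week 12 is only an example, since the documents give no reason to prefer one visit. The sponsor must supply the score and the starting point. This keeps alpha at 0.05 and power at 95.4% with 41 evaluable per arm.

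One pre-specified longitudinal between-group test would serve equally well. A t-test of the three-visit mean, with effect size d/√((1 + 2ρ)/3), has power 0.999, 0.994, 0.983 and 0.965 at ρ = 0.3, 0.5, 0.7 and 0.9.

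Report the remaining visits and the three secondary scales as estimates with 95% confidence intervals.

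If all three visits stay co-primary with any one sufficing, use Bonferroni or Holm and restate power for the rule chosen. Bonferroni at 0.05/3 = 0.0167 gives about 89% power at a single visit with 41 per arm. Over ρ from 0.9 to 0.3, Holm gives about 94% to 99% for at least one visit and 92% to 94% on average per visit.

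The cost is one or two sentences in each of the three sections and no extra patients. The small downside is that significance only at a non-primary visit would no longer count as primary success.
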